5.1.1.4 Mapping of assessments performed at Early Termination Visit

Safety assessments made at an early termination visit that correspond to a scheduled visit will be summarized at the scheduled visit to corresponding to the early termination visit if the assessment was scheduled to occur at that visit. Such assessments at the early termination visit will also be considered for safety follow up/ termination visit.

5.1.1.5 Definition of Baseline values

Unless otherwise stated, a Baseline value refers to the last non-missing value collected prior to the first treatment. Scheduled or unscheduled measurements can be used as the Baseline value. If a Baseline measurement is repeated and is obtained prior to the first treatment, then the last available measurement will be used as the Baseline value. If an unscheduled measurement occurs

after the planned Baseline measurement time point but before the first treatment, then the unscheduled measurement will be used.

Table 5-2: Definition of Baseline for Part A and Part B

Procedure	Baseline Day
Vital sign	Predose on Day 1 or if missing then the Baseline data will be missing.
Single 12-lead ECG	
Laboratory assessments (hematology, clinical chemistry, and urinalysis)	Baseline is defined as the value on Day -1. If this value is missing, the most recent value obtained prior to Day 1 will be used as Baseline.

ECG= electrocardiogram

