**Table 1-3: Part A Schedule of activities**

Procedure	Screening	Treatment Period 1—6 a													SFU b / ETV
		In-Clinic Period													
	D-28 to D-2	D-1	D1	D2 to D5	D6	D7 to D10	D11	D12 to D18 c	D19	D20 to D23	D24	D25 to D28	D29	D30 to D33	Day 37 (± 2 days)

c The blood pregnancy test will be done at the Screening Visit and the urine pregnancy test will be done on all other occasions.

f Blood hematology and chemistry laboratory tests will be obtained in the fasting state following an overnight fast of at least 10 hours. Urinalysis includes standard analysis, microscopy, and renal biomarker analysis. For the AKI biomarkers, analysis should be performed on the fresh urine sample. Spot analysis will be performed on either fresh urinalysis sample or 24 hours urine sample, as noted.

g Only performed on Day 14 and Day 33.

h A COVID-19 test will take place per site standard to allow flexibility in the event the COVID-19 response plan changes throughout the study (ie, frequency of testing).

i During the Screening Period, at Baseline (only if the ECG was done more than 3 days before screening [between D-28 and D-2, inclusive]), and on Day 1, the 12-lead ECG (single recordings) will be performed after a rest of at least 10 minutes predose and 2 hours after dosing. If there are abnormalities that are considered clinically significant for a particular study participant, ECG recordings will be performed in triplicate at 2- to 3-minute intervals (3 ECGs within a 5-minute timeframe) prior to the exclusion of the participant (Section 7.1.2).

j Systolic and diastolic blood pressure, respiration rate, pulse rate, and tympanic body temperature will be assessed. Vital signs will be performed after a rest of at least 5 minutes predose, then 30 min, and 2 hours after study medication dosing on Day 1, Day 6, Day 11, Day 19, Day 24, and Day 29. Vital signs (to be taken before blood collection for laboratory tests) will consist of 3 pulse rates and 3 blood pressure (BP) measurements (3 consecutive BP readings will be recorded at intervals of at least 1 minute).

k An IRT will be used for assigning eligible participants to a treatment regimen based on a predetermined production randomization and/or packaging schedule provided by UCB (or designee) (Section 6.3).

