f Systolic and diastolic blood pressure, respiration rate, pulse rate, and tympanic body temperature will be assessed. Vital signs will be performed after a rest of at least 5 minutes. On Day 1 and Day 6, vital signs will be measured predose, then 30 minutes, 2 hours, and 24 hours after study medication administration.

g An IRT will be used for assigning eligible participants to a treatment regimen based on a predetermined production randomization and/or packaging schedule provided by UCB (or designee) (see Section 6.3). Study participants will receive 3 dose levels (90mg, 180mg, and 360mg) of UCB0599 or placebo under normal gastric pH conditions. The Washout Period will take place after each period and last for 4 days. See Section 4.1 for details on the overall study design of Part B.

h The PK sampling time points will be done at predose and at 0.25, 0.5, 1, 1.5, 2, 4, 8, 12, 24, 36, 48, 72, and 96 hours after UCB0599 administration.

i Genetic blood sampling will be mandatory for study participation and will be performed on Day 1 (Section 8.7).

j Study participants will receive standard meals and snacks at appropriate times as indicated by the clinic center, except for when they are required to fast.

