### **9.5 Planned safety and other analyses**

#### **9.5.1 Safety analyses**

Unless stated otherwise, all safety analyses will be performed on the SS.

All AEs will be coded using the most recent Medical Dictionary for Regulatory Activities (MedDRA®) and characterized as pretreatment and treatment emergent according to the intake of the study medication.

The occurrence and incidence of TEAEs will be summarized by MedDRA system organ class (SOC), HLT, and preferred term (PT), and by treatment and ethnic group (for Part B only). The occurrence and incidence of TEAEs will also be summarized by maximum event intensity and by relationship to the study medication. Adverse events will be categorized by severity (mild/moderate/severe). All AEs will be listed and will include actions taken for each AE, the time of onset of the AE after dosing, and the duration of each AE. Adverse events leading to discontinuation and SAEs will also be summarized by treatment group and ethnic group.

Laboratory variables and changes from Baseline will be summarized by time point and will be presented by treatment and ethnic group. For categorized values according to the reference range, shift tables from Baseline (Day -1, or Day 1 prior to first treatment) to each post-Baseline

time point will be presented for selected variables to be defined in the SAP. Values outside the reference range will be flagged in the listings.

Vital sign variables (SBP and DBP, pulse rate, respiration rate, and body temperature) and changes from Baseline (Day -1, or Day 1 prior to first treatment) will be summarized by time point and will be presented by treatment and ethnic group.

Single 12-lead ECGs will be recorded at each time point as noted in the study Schedule of Activities (Section 1.3). Descriptive statistics will be presented for ECG values and changes from Baseline (Day -1, or Day 1 prior to first treatment) over time.

See Section 9.8 for details on planned interim analyses and data monitoring.

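### SAP Table 5-2 gives vital signs (and apparently ECG) no fallback when the Day 1 predose value is missing, although the protocol and the SAP's own general rule would let an earlier pre-treatment value serve as Baseline

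*SAP*

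**What the plan says.** SAP 5.1.1.5 (Definition of Baseline values) opens with a general rule that applies unless otherwise stated: "a Baseline value refers to the last non-missing value collected prior to the first treatment". Scheduled and unscheduled measurements both qualify.

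Table 5-2, in the same section, then sets rules by assessment:

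- **Vital signs:** "Predose on Day 1 or if missing then the Baseline data will be missing".
- **Single 12-lead ECG:** the cell is blank in the extracted text. A cell merged with the vital-sign row is the natural reading, but it is an inference.
- **Laboratory:** the Day -1 value, with a fallback: "If this value is missing, the most recent value obtained prior to Day 1 will be used as Baseline".

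Protocol 9.5.1 says of vital signs that "changes from Baseline (Day -1, or Day 1 prior to first treatment) will be summarized by time point", and of ECG: "Descriptive statistics will be presented for ECG values and changes from Baseline (Day -1, or Day 1 prior to first treatment) over time".

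SAP 6.4 (Changes to Protocol-Planned Analyses) is marked as not applicable.

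**The concern.** Where the protocol names two acceptable Baseline days for vital signs and ECG, the SAP keeps one and sets Baseline to missing if that one is absent. No reason is given, and the laboratory row of the same table is treated more generously. The change is not listed among departures from the protocol.

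Changes from Baseline in vital signs and ECG are listed as Other safety endpoints in Part B (Protocol Table 3-2), where each cell of the summaries is small. A participant with a usable earlier pre-treatment value would be left out of those summaries for want of one reading.

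**Working it through.** The plan states no figure here that could be reproduced. The check compares the rules and counts scheduled measurements.

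**1. The rules side by side, when the Day 1 predose value is missing**

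| Source | What happens |
|---|---|
| Protocol 9.5.1 (vital signs, ECG) | Day -1 is also a named Baseline day |
| SAP 5.1.1.5, general rule | Last non-missing earlier value is used |
| SAP Table 5-2, vital signs | Baseline is missing |
| SAP Table 5-2, ECG | Baseline is missing, if the cell is merged |

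The laboratory row anchors on Day -1 and falls back to an earlier value if that is missing.

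**2. Is there a value to fall back on?**

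- Vital signs: yes. They are scheduled at Screening and on Day -1 in both parts (Protocol Tables 1-3 and 1-4).
- ECG: not always on Day -1. The ECG footnotes to both tables make the Day -1 recording conditional on the timing of the earlier one. Where it was not done, the fallback is the screening ECG.

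**3. Size in Part B**

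Protocol 4.1.2 gives, per ethnic group, 4 active participants in each of Sequences 2, 4 and 6. Each dose occurs in two of these sequences:

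- 90mg: Sequences 2 and 6, 4 + 4 = 8
- 180mg: Sequences 2 and 4, 4 + 4 = 8
- 360mg: Sequences 4 and 6, 4 + 4 = 8

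SAP 5.5.3.2.1 and 5.5.3.3.1 summarize by time point, dose level and participant group. Each active participant contributes at two doses, so one missing Day 1 value removes 1/8 = 12.5% of the ethnic group at each of two doses. Placebo has 1 + 1 + 1 = 3 participants per ethnic group and is pooled (SAP Table 5-4), so one loss there is 1 of 3.

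**4. Size per participant**

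For vital signs in Part A, the schedule is predose, 30 minutes and "2 hours after study medication dosing on Day 1, Day 6, Day 11, Day 19, Day 24, and Day 29", plus the Safety Follow-Up visit. After the first dose that gives 2 (Day 1) + 5 × 3 (later periods) + 1 (follow-up) = 18 change values. All 18 are lost if the Day 1 predose value is missing, even when a Day -1 value exists.

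For ECG in Part B (Protocol Table 1-4, ECG footnote), the values after the first dose are Day 1 at 2 hours, Day 2, Day 6 predose, Day 6 at 2 hours, Day 7 and follow-up: 6 change values. Their change-from-Baseline QTcF categories in SAP 5.5.3.3.1 are lost with them.

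**5. Values available for an optional same-period change**

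| Assessment | Scheduled predose values, Part A | Scheduled predose values, Part B |
|---|---|---|
| Vital signs | 6 | 2 |
| ECG | 1 (Day 1 only) | 2 |

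For vital signs in Part B: "On Day 1 and Day 6, vital signs will be measured predose". Against the Day 1 Baseline, Part A Periods 4 to 6 are compared with a value 19 − 1 = 18, 24 − 1 = 23 and 29 − 1 = 28 days old, taken before esomeprazole starts on Day 14. In Part B, each dose is given in Period 1 to 4 of the 8 active participants and in Period 2 to the other 4, whose Baseline is then 6 − 1 = 5 days old and precedes a different dose.

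**The case against.** **The exception is announced.** The general rule yields where something else is stated, so Table 5-2 may override it. The phrase in Protocol 9.5.1 can also be read as naming two possible Baseline days, which the SAP then allocates: Day -1 to laboratory data, Day 1 predose to vital signs. On that reading the protocol does not spell out a fallback. This has some force: it softens the conflict with the protocol. It does not explain why laboratory data get a fallback and vital signs do not, or why a usable earlier value should be set aside.

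**The consequence is small.** Participants are confined from Day -1 at one site and dosed by staff, so a missed predose reading should be uncommon. The endpoint is listed under Other in Part B, is not a listed endpoint in Part A, and is summarized descriptively. All of this stands, and it sets the weight of the point.

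**Stronger readings that the documents do not support:**

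- A reader might infer that using one Day 1 value for all periods departs from the protocol. It does not: Protocol 9.5.1 also uses a single pre-treatment Baseline and asks for no period-specific one. A fixed Baseline shows cumulative change, while a Period 2 predose value already follows a first dose. Both are legitimate.
- A reader might infer that later predose readings are thrown away. SAP 5.5.3.2.1 and 5.5.3.3.1 summarize observed values as well as changes by time point. Those readings are only not used as Baseline.
- A reader might infer that same-period predose ECGs exist throughout. In Part A none is scheduled after Day 1.
- A reader might infer that the participant leaves every change-from-Baseline table. The loss is confined to the assessment concerned: laboratory changes have their own rule, a missing vital-sign value does not affect ECG, and absolute QTcF categories remain.

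**Conclusion.** The point holds in a narrow form. For vital signs, Table 5-2 refuses a fallback that the SAP's general rule provides, that the laboratory row has in kind, and that Protocol 9.5.1 allows on its plain reading; SAP 6.4 does not declare the narrowing. For ECG the same follows only if the blank cell is merged with the row above.

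The cost is conditional: for each missed Day 1 predose value, 1 of 8 active participants in the ethnic group at each of two Part B doses, for that assessment. The documents give no rate of missed values, so no expected loss can be computed; with none missed, the loss is nil. This is a minor improvement, not a threat to any conclusion of the study. The lack of a same-period Baseline is a design preference, not an error.

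**What to change.** In SAP Table 5-2, replace the vital-sign rule with: *last non-missing value before first treatment (Day 1 predose; if missing, the most recent earlier value)*. State the same rule explicitly in the ECG row, noting that the ECG fallback may be the screening recording. If the sponsor prefers the narrower rule, declare it in SAP 6.4 with a reason.

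Optionally, add change from same-period predose for vital signs (both parts) and for ECG (Part B only), as a supplement to the study-level Baseline summaries.

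The cost is one line of SAP wording and a small change to the Baseline derivation; the option needs one extra derived variable. The values are already scheduled, so no new data collection is needed.

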5.1.1.2 Protocol Deviations

Protocol deviations are specified in Appendix 1 (Section 6.1.2).

All protocol deviations will be reviewed at the Data Cleaning Meetings (DCM) and decisions made on whether they should be considered important or not.

Important protocol deviations (IPDs) are deviations from the protocol which could potentially have a meaningful impact on study conduct or on either the primary or key secondary outcome(s) for an individual study participant. The criteria for identifying such protocol deviations will be defined within the IPD specifications document.

Important protocol deviations will be categorized as follows:

2. Inclusion/exclusion criteria deviations
3. Incorrect treatment or dose administered
4. Procedural non-compliance
5. Prohibited concomitant medication use
6. Withdrawal criteria deviation

All IPDs will be reviewed as part of the ongoing data cleaning process and data evaluation. At least one Data Evaluation Meeting (DEM) will be performed prior to the final database lock after all data have been verified/coded/entered into the database to discuss exclusion of study participants from analysis populations.

Participants may be excluded from the safety set if they do not pass the inclusion/exclusion criteria. However, should a participant be mistakenly dosed despite failing the inclusion/exclusion criteria, then their safety data would need to be reported as part of the safety analysis. Participants may be excluded from other analysis sets, but this will be determined on a case-by-case basis. If the deviation is deemed to have the potential to bias the analyses for the duration of the study then the whole participant may be removed in a sensitivity analysis on the key endpoints. The removal of the participant and the rationale will be clearly documented within the relevant TFLs.

Important protocol deviations will be identified and classified by the deviation types in the IPD document. A listing of all IPDs identified at the DCMs will be presented for all participants based on the safety set and will include the deviation type and description.

The IPDs will be tabulated using the SS, separately for Part A and Part B and will present the deviation type and description by treatment group.

5.1.1.3 Treatment assignment and treatment groups

It is expected that participants will receive treatment as randomized; hence safety analyses will be based on the SS-as randomized. However, if after unblinding it is determined that participants received treatment other than what they were randomized to, then for PK and safety analyses purposes participants will be allocated to the actual treatment they received (SS-as treated).

5.1.1.4 Definition of Analysis by Variables

Table 5-3: Definition of Analysis by Variables for Part A

Term	Variables
Sequence	Sequence 1 (ABC)
	Sequence 2 (ACB)
	Sequence 3 (BCA)
	Sequence 4 (BAC)
	Sequence 5 (CAB)
	Sequence 6 (CBA)
Formulation	180mg (90mg x 2 granules in capsule)
	180mg non-encapsulated tablet containing PPD
	180mg encapsulated tablet containing PPD
Gastric condition	Normal gastric pH
	Elevated gastric pH

Note: A: 180mg (90mg x 2 granules in capsule) current clinical formulation (reference formulation); B: 180mg non-encapsulated tablet containing PPD ; C: 180mg encapsulated tablet containing PPD .

Table 5-4: Definition of Analysis by Variables for Part B

Term	Variables
Sequence	Sequence 1 (C=1, J=1; 90mg → 180mg)
	Sequence 2 (C=4, J=4; 90mg → 180mg)

Table 5-4: Definition of Analysis by Variables for Part B

Term	Variables
	Sequence 3 (C=1, J=1; 180mg → 360mg)
	Sequence 4 (C=4, J=4; 180mg → 360mg)
	Sequence 5 (C=1, J=1; 360mg → 90mg)
	Sequence 6 (C=4, J=4; 360mg → 90mg)
Dose level	Pooled Placebo
	90mg
	180mg
	360mg
Participant group	Japanese participants
	Chinese participants
	Part A healthy participants under normal gastric pH condition on the formulation chosen for Part B

C=Chinese participants; J=Japanese participants.

Table 5-5: Analysis Performed by “by Variables”

Analysis	Part A by Variable	Part B by Variable
Disposition	Sequence	Sequence
Medical History		
Concomitant Medications		
Important Protocol Deviations		
PK Concentration	Formulation and gastric condition	Dose level and participant group
Adverse Events	Formulation	Dose level and participant group
Laboratory Values	Time Point and Sequence	Time Point Sequence
Vital Signs		
ECG		

ECG= electrocardiogram; PK=pharmacokinetic.

5.1.1.5 Center pooling strategy

This is a single center study.

5.1.1.6 Coding dictionaries

Medical history and adverse events (AEs) will be coded using the current version of Medical Dictionary for Regulatory Activities (MedDRA) at time of database lock. Medications will be coded using the current version of World Health Organization Drug Reference List (WHO-DRL) at time of database lock. Medical procedures will not be coded.

5.1.1.7 Handling of repeated and unscheduled measurements

All repeated and unscheduled measurements will be presented in the data listings, where applicable. Repeated measurements are defined as more than 1 measurement at same time point. The following general rules will apply to all repeated and unscheduled measurements:

- For repeated measurements obtained prior to the first dose of study medication the latest value (which may be scheduled or unscheduled) will be used in the calculation of the descriptive statistics.
- For repeated measurements obtained for the designated Baseline value, the latest value (which may be scheduled or unscheduled) will be defined as the Baseline provided that this occurred prior to the first dose of study medication.
- Unscheduled measurements and repeated measurements after the first one at a given time point will not be used in the descriptive statistics at time points after first dose of study medication.
- Unscheduled measurements performed for the Early EOS/WD visit will be assigned to the EOS Visit and analyzed accordingly as an EOS Visit.

5.2 Participant Dispositions

Participant screening and primary reason for screen failure will be summarized using the ASPS, separately for Part A and Part B. The summaries will include the following:

- Number of participants screened
- Number and proportion of participants rescreened
- Number and proportion of participants with screen failures (Not counting successfully rescreened participants)
- Number and proportion of screen failures by primary reason for screen failure (Based on the later screening visit)

By-participant listings of rescreened participants will be presented using the ASPS.

Participant disposition will be summarized using the ASPS, separately for Part A and Part B. Each summary will include the following:

- Date of first screening visit
- Date of last visit for last participant
- Number of participants screened
- Number of participants in each analysis set, by treatment sequence (according to randomized treatment).

Disposition of analysis sets will be tabulated using the ASPS, separately for Part A and Part B. Each table will present the total number of participants in the ASPS, as well as the number and percentage of participants in each analysis set by treatment sequence.

Study completion/discontinuation and primary reason for discontinuation will be summarized using the RS, separately for Part A and Part B. Each table will present the following, by treatment sequence:

- Number and percentage of participants that started the study
- Number and percentage of participants completing the study
- Number and percentage of participants discontinuing the study
- Number and percentage of participants discontinuing the study by primary reason for discontinuation.
- Part A only:
 - Number and percentage of participants that started substudy 1 and substudy 2
 - Number and percentage of participants completing substudy 1 and substudy 2
 - Number and percentage of participants discontinuing substudy 1 and substudy 2

Participants that started the study are defined as participants that were randomized. Participants completing the study are those participants completing the SFU visit AND who did not discontinue dosing or withdraw from the study for any reason before the SFU.

Participants that started substudy 1 and substudy 2 are defined as participants who started treatment period 1 and 4, respectively. Participants completing the substudy 1 and substudy 2 are those participants completing Washout period 3 and 6, respectively.

Study discontinuation due to AEs will be tabulated using the RS, separately for Part A and Part B. Each table will present the number and percentage of participants who discontinued the study due to AE by treatment sequence.

By-participant listings of participant who did not meet study eligibility criteria will be presented by study part and treatment sequence, using the ASPS. The listing will include inclusion criteria that were not met and the exclusion criteria that were met.

By-participant listings of participant disposition will be provided using the ASPS, by study part and treatment sequence. The listings will include:

- Study termination/completion status
- Date of informed consent
- Date of randomization
- Date and time of first study treatment (first start date and time)
- Date and time of last study treatment (last stop date and time)
- Date of last contact

- Date of premature study termination for successfully screened participants dropping out of the study.
- Date of screen failure for screen failure participants (based on the last screening visit in case of rescreen)
- Primary reason for premature study termination
- Primary reason for screen failure (Based on the last screening visit in case of rescreen)

By-participant listings of participant inclusion in each analysis set will be presented by study part and sequence, using the ASPS.

By-participant listings of study discontinuation will be presented by study part and sequence, using the RS.

